RESEARCH PROTOCOL

Continuous Glucose Monitoring for Hyperglycemia in Critically Ill Patients

NCT05442853

October 20, 2022

RESEARCH PROTOCOL

1. **Project Title:** Continuous Glucose Monitoring for Hyperglycemia in Critically III Patients

2. Abstract:

The investigators intend to conduct prospective, randomized comparative trial of patients admitted to the intensive care unit (ICU) at the North Florida/South Georgia Veterans Health System who received continuous glucose monitoring (CGM) vs standard glucose monitoring. This study will examine several outcomes for patients in the ICU with hyperglycemia. The primary outcome of the study will be the percentage of time in target range (blood glucose 70-180 mg/dL). Secondary outcomes will include percentage of time in clinically significant hypoglycemic (BG < 54 mg/dL), hypoglycemic (BG 54-69 mg/dL), hyperglycemic (BG 181-250 mg/dL), and clinically relevant hyperglycemic (BG >250 mg/dL) ranges; ICU length of stay, ICU mortality, 30-day mortality, costs associated with monitoring, mean BG, glucose variability between the two groups (% coefficient of variation = SD/mean BG*100%), and patient satisfaction. An evaluation will be done to assess the proportions of patients with new infection, acute kidney injury (AKI), agitation, delirium, and pain. Correlation between CGM values and whole blood values for blood glucose will be evaluated.

3. Background:

Diabetes mellitus (DM) is a common comorbidity among hospitalized patients with over 25% reporting a history of the disease. Furthermore, stress-induced hyperglycemia is common in critically ill patients. Among these patients, glucose control is a necessity to avoid further complications. Inpatient hyperglycemia has been associated with a longer length of stay, increased risk of infection, and increased mortality. Hypoglycemia can be more severe in hospitalized patients and can also increase length of stay and mortality. The current standard for glucose monitoring involves point-of-care (POC) blood glucose finger sticks or arterial/venous whole blood sampling. These methods have limitations and continuous glucose monitors (CGMs) offer a potential alternative.

Continuous glucose monitors (CGMs) were originally designed for use in the home and outpatient setting, with less data on its application in the hospital or critical care settings. Until April 2020, CGMs were not approved for inpatient use. To support COVID-19 healthcare efforts, the FDA allowed for the use of continuous glucose monitoring (CGM) systems for the treatment of patients in various healthcare facilities. This remote glucose monitoring allowed for conservation of personal protective equipment (PPE) and reduction of potential exposure of staff from multiple point-of-care glucose checks. Compared to the POC checks every one to two hours, CGM systems can provide blood glucose readings multiple times each hour, allowing for remote monitoring and the ability to detect urgent changes in blood glucose.

Several studies have evaluated the use of CGM among hospitalized patients with DM and have shown positive results when compared to traditional POC glucose

monitoring. Most studies have found the use of CGM can help minimize the number of hypoglycemia episodes and overall improve patient care. Similar studies have been done in the intensive care unit (ICU) with favorable results; however, these studies had smaller sample sizes and limited external validity. While there is consensus on the superiority of CGM detecting hypoglycemic blood glucose levels, the effects on other patient outcomes in the critically ill remain uncertain.

4. Study Purpose:

The purpose of this study is to compare the use of CGM versus POC glucose monitoring in the critical care setting for differences in glycemic control and other important ICU outcomes.

5. Research Plan:

a. Study Design:

i. Prospective, single-center, randomized comparative trial

b. Study Sample:

- Adult patients at North Florida/South Georgia Veterans Health System anticipated to be admitted to an ICU for a minimum of 48 hours after enrollment
- A minimum sample size was calculated to be a total of 88 patients (44 per group), but will continue to enroll patients for a maximum of 2 years or a maximum of 300 patients
 - 1. Anticipated mean POC % time in range of 58% (based on current rates in our facility) with a standard deviation of 20%
 - 2. Anticipated mean CGM % time in range of 70% (based on CGM interpretation guidelines)
 - 3. 80% power, 5% alpha

c. Inclusion Criteria:

- i. Patients age 18-89
- Past medical history of any diabetes mellitus OR patients with at least 1 measured BG of 180 being treated with insulin (subcutaneous or infusion)
 - 1. Enrollment will occur within 72 hours after being admitted to an ICU if history of diabetes
 - 2. Enrollment will occur within 72 hours after developing hyperglycemia in ICU if no diabetes

d. Exclusion Criteria:

- i. Pregnant patients
 - Female patients who report no known current pregnancy, will be considered to not have potential to be pregnant with one of the following:

- a. History of surgical sterilization (methods include hysterectomy, bilateral tubal ligation, bilateral salpingectomy or bilateral oophorectomy)
- b. Postmenopausal (defined as age greater than 62 years, or age 62 years or less than with amenorrhea for at least 12 consecutive months)
- c. No sexual partners within previous 9 months who can father children (those who cannot father children include female partners; and male partners who are incapable of fathering children because of congenital anomalies, surgery, or medical treatment)
- d. Reported consistent use of hormonal (oral contraceptives, implant, injection, patch, vaginal ring) or intrauterine device (IUD) contraception.
- ii. Diagnosis of diabetic ketoacidosis (DKA)
- iii. Diagnosis of hyperosmolar hyperglycemic state (HHS)
- iv. Anticipated to require prone positioning while on insulin therapy
- v. Any contraindications to CGMs based on manufacturer labeling
- vi. BG above maximum reading for CGM (e.g. greater than 400 mg/dL)
- vii. Receiving medication that could interfere with CGM readings (based on manufacturer specifications)
 - 1. Receiving any dose of hydroxyurea as this could falsely elevate the sensor readings (if applicable for specific CGM)
 - Receiving greater than 1,000mg acetaminophen every 6 hours in any form as this could falsely elevate the sensor readings (if applicable for specific CGM)

e. Recruitment:

- Patients who meet eligibility criteria for this study may be referred to the study team by a clinical staff member of the ICU team responsible for the clinical care of the patient. Study team members are ICU clinicians and may also be part of the team providing clinical care.
 Patients (or their authorized decision maker) will first be asked if they wish to learn about the study. If the patient is interested in participating in the study, the research team will contact the patient and provide details of study participation and informed consent.
- ii. Patients will be provided information on standards of care. As a participant in this study, all care including medical procedures, diagnostic tests, monitoring, medications, treatments, and other care will be the same for all patients as those who do not participate in the study, with the exception of the method of glucose monitoring.

f. Randomization:

- i. Study participants will be randomly assigned to one of the study groups after being found eligible for inclusion and giving consent to participate
- ii. A randomization process, such as a computerized algorithm or random number generator will be used to assign patients a group upon inclusion
- iii. Patients will be allocated 1:1 to the monitoring groups based on this randomization

g. Study Groups:

- i. Group 1: POC group (Blinded to CGM)
 - 1. All patients will have Dexcom G6 Pro CGM sensor/transmitter placed per device instructions
 - 2. Nurses and all members of the medical treatment team will be BLINDED to the CGM blood glucose readings during the study period
 - 3. Glycemic management will be based on POC glucose values.
- ii. Group 2: CGM group (Unblinded to CGM)
 - 1. All patients will have Dexcom G6 CGM sensor/transmitter placed per device instructions
 - 2. Nurses and all members of the medical treatment team will be UNBLINDED to the CGM blood glucose readings during the study period
 - 3. Glycemic management will be based on CGM values.

h. Study Outcomes

i. Primary Outcome

- Percentage of time in target range (BG 70-180mg/dL) [Appendix E]
 - a. Comparison of CGM readings between both types of monitoring/treatment groups

ii. Secondary Outcomes

- Percentage of time in each range (Appendix E) [Comparison of CGM readings between both types of monitoring/treatment groups]
 - a. Clinically significant hypoglycemic range (BG < 54 mg/dL)
 - b. Hypoglycemic range (BG 54-69 mg/dL)
 - c. Hyperglycemic range (BG 181-250 mg/dL)
 - Clinically relevant hyperglycemic range (BG >250 mg/dL)
- 2. ICU length of stay
- 3. ICU mortality
- 4. 30-day mortality

- 5. Costs associated with monitoring
- 6. Mean BG
- 7. Glucose variability for each group
 - a. % coefficient of variation = SD/mean BG*100%
- 8. Patient satisfaction

iii. Safety

- 1. Proportion of patients with a new infection
- 2. Proportion of patients with new AKI (AKIN guidelines)
- 3. Proportion of patients with CAM-ICU positive delirium
- 4. Proportion of patients with agitation (RASS \geq 2)
- 5. Proportion of patients with a positive pain score (CPOT vs DVPRS)
 - a. Correlate pain score with timing of BG check for POC and at time of placement of CGM

i. Inpatient Hyperglycemia Management:

- i. Hyperglycemia management will be directed by the ICU team per standard of care
- ii. Standard nutritional guidelines are recommended. Nutritional care will be managed at the discretion of the providers
- iii. IV insulin infusion targeting BG 140-180 mg/dL is preferred treatment, especially if NPO, on an inconsistent nutritional regimen, hemodynamically unstable, or in setting of organ dysfunction
 - Will use validated protocol with computerized decision support tool (Appendix D)
 - 2. Converting from IV insulin infusion to SC insulin managed as described in Appendix D
- SC insulin regimen may be used based on the discretion of the treating ICU team, with dosing/agents recommended in Appendices A, B, and C
 - 1. Only recommended for patients on consistent nutritional regimen who are hemodynamically stable
 - Daily insulin dose adjustments to the SC insulin regimen will be managed at the discretion of the treating ICU team, considering use of correctional insulin and concomitant factors (e.g. use of medications which increase blood glucose)

j. Hypoglycemia Management:

- i. Managed per protocol in both groups.
 - 1. If able to eat/swallow, 15 grams of carbohydrates (glucose tablets/glucose gel) PRN
 - 2. If unable to eat/swallow or developed severe hypoglycemia, ½ ampule vs 1 ampule intravenous D50W PRN

- 3. If no intravenous access is available, 1mg glucagon subcutaneous PRN
- ii. Additional treatment may be given after 15 minutes if the patient has an inadequate response to the glucose correction.

k. CGM Devices:

- Two CGM devices will be used in this study, Dexcom G6 and Dexcom G6 Pro. Both devices are placed similarly onto patients. Both devices can be worn for same timeframe (10 days). Both devices can interact with same applications, smartphone, and manufacturer software (Dexcom Clarity). Both devices carry same manufacturer instructions for placement and use with specific medications and diagnostic procedures. Dexcom G6 can only be used in an Unblinded mode where CGM values are visible to the patient and clinical care team. Dexcom G6 Pro allows for a Blinded mode where CGM values are not visible to patients or the clinical care team.
- ii. Dexcom G6
 - 1. Will be used in the CGM group
 - 2. Used only in Unblinded mode
 - 3. Sensor and transmitter are separate components
- iii. Dexcom G6 Pro
 - 1. Will be used in the POC group
 - 2. Will be used in Blinded mode
 - 3. Sensor and transmitter are combination device

I. Blood Glucose Correlation:

- i. CGMs will be calibrated if necessary, per manufacturer instructions with POC or venipuncture BG sample
- ii. CGM and POC tests will be correlated with routine venipuncture monitoring on at recommended daily interval unless clinical suspicion of an inaccurate reading

m. POC Group Procedures:

- i. CGMs will be placed on the abdomen (or other site) per manufacturer recommendations and can be at the discretion of placing provider.
 - a. Placement at least 3 inches from insulin pump infusion or injection site
 - b. Placement away from waistband, scarring, tattoos, irritation, and bones
 - c. Placement in a location unlikely to be bumped, pushed, or laid on while sleeping
 - d. CGMs will be removed prior to any surgery, computed tomography (CT) scan, or magnetic resonance imaging

(MRI), or other procedure as necessary per manufacturer instructions

- ii. Patients, nurses, and other treatment team will be blinded to the CGM readings
 - 1. All treatment decisions for this group will be based on POC readings and venipuncture
- iii. POC BG will be checked per protocol based on treatment received
 - 1. Every 1-2 hours per protocol if receiving an insulin infusion
 - 2. At least 3 times per day if receiving a basal:bolus insulin regimen

n. CGM Group Procedures:

- i. CGMs will be placed on the abdomen (or other site) per manufacturer recommendations and can be at the discretion of placing provider.
 - a. Placement at least 3 inches from insulin pump infusion or injection site
 - b. Placement away from waistband, scarring, tattoos, irritation, and bones
 - c. Placement in a location unlikely to be bumped, pushed, or laid on while sleeping
 - 2. Remote monitoring software will be set up for nursing staff
 - 3. All staff will be educated on using the monitoring software
 - CGMs will be removed prior to any surgery, computed tomography (CT) scan, or magnetic resonance imaging (MRI), or other procedure as necessary per manufacturer instructions
- ii. Nurses and treatment team will NOT be blinded to the CGM readings
 - 1. All treatment decisions for this group will be based on CGM readings, confirmatory POC readings (as necessary), and venipuncture
- iii. Nursing staff will obtain a confirmatory POC for hypoglycemia alarms and administer appropriate therapy per protocol
 - 1. If a different reading is recorded, a venipuncture will be obtained
- iv. CGMs will record the BG and transmit to a remote device
 - The duration of CGM use for the study will be limited to 10 days (or the maximum duration allowable for use as recommended by the manufacturer)
- v. CGMs are pre-set with the following alerts:
 - 1. Low-glucose alerts set to 70 mg/dL
 - 2. Urgent low alerts set to 55 mg/dL, with urgent low soon alerts set if BG is expected to be 55 mg/dL within 20 minutes
 - 3. High alerts set to 250 mg/dL

- vi. BG readings less than 40 mg/dL are read on the CGMs as "LOW".While the exact reading will be unable to be determined, the amount of time spent in the "LOW" reading will be recorded
 - 1. When this occurs, a confirmatory POC reading will be obtained. If these numbers differ, a venipuncture will be collected

o. Data Collection

- i. CGM Sensor Data
 - 1. Clinical CGM data will be transmitted and evaluated using manufacturer software.
- ii. The following will be obtained from the Computerized Patient Records System (CPRS):
 - 1. **Demographic Data:** age, sex, race, weight, height, comorbidities
 - 2. Admission Data: length of stay, diagnoses, mortality
 - 3. Clinical Data: vital signs, complete metabolic panel (BMP) and other serum electrolytes (magnesium/phosphate), complete blood counts, liver function tests, infection/microbiology results (gram stains/cultures/sensitivities/PCR or other microbiology identification), blood gases, other laboratory data need to assess treatment/diagnoses/severity of illness, blood glucose levels, antidiabetic treatments (including type of insulin and doses administered), other medications (including presence of additional medications [e.g. steroids, vasopressors, or any other medications that may affect blood glucose or the CGMs sensors]), sedation/agitation (e.g. Richmond Agitation Sedation Scale) scores, delirium (e.g. CAM-ICU) scores, pain (e.g. CPOT, DVPRS) scores, diet/nutritional regimen
- iii. Satisfaction survey data: patient satisfaction survey
- iv. **Cost Analysis:** a comparison will be conducted based on the costs of equipment, staff time, and other relevant costs related to glucose monitoring in each group

p. Privacy, Security, and Confidentiality:

- i. Investigators will be responsible for maintaining patient privacy and confidentiality
- ii. The principal investigator has the responsibility for security of the study
- iii. Study data will be entered, managed, and stored securely using VA Research Electronic Data Capture (REDCap).
- iv. Study data will be coded then de-identified for data analysis.

6. Analysis Methods:

Descriptive statistics and inferential statistical methods will be used as appropriate to report findings of this study.

To minimize risk of bias, data collection and analysis will be by performed by study team members not involved in the clinical care of the study participants, as possible.

7. Possible Discomforts and Risks:

- Inaccurate measurement of BG which could lead to hypo- and hyperglycemia
- CGMs are minimally invasive but could cause some patients mild physical pain or discomfort
- Apart from the type of monitoring utilized, no further changes to patient care will be made. Investigators will not alter medication prescribing to deviate from standard of care. As such, no additional discomfort or risk to the patient caused by this study is expected.

8. Possible Benefits:

- Reduction of serious hypoglycemia or other adverse events is the most relevant potential benefit of using CGM
- Decreased point-of-care finger sticks compared to standard care. This may lead to benefits such as increased patient comfort and reduced costs.
- Possible benefit of improved glycemic control with the ability to monitor glucose levels more carefully and adjust treatment as appropriate; this could lead to improved patient outcomes. We hypothesize the use of CGM will yield less cases of hypoglycemia and more glucose values at goal.

9. Anticipated Costs:

GGM devices and other necessary equipment will be provided through a manufacturer sponsored grant. Administrative and regulatory expenses will be covered by a manufacturer sponsored grant. No other costs beyond investigator salary and those for routine clinical care are anticipated.

10. Conflicts of Interest:

None of the investigators hold a patent or license for any material, object, or process involved with this research. None of the investigators own stock in or serve as consultants to any company involved in this research. The researchers will not receive payment or other financial incentive for conducting this study.

The PI or any of the Sub-investigators have no real or potential conflict of interest with regards to this research project.

11. References:

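### Insulin route at enrollment plausibly predicts time in range but is neither a stratum in 5.f nor a covariate in section 6, which costs precision at 88 patients

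*Combined protocol and SAP*

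**What the plan says.** **Assignment.** Section 5.f says of the method: "A randomization process, such as a computerized algorithm or random number generator will be used to assign patients a group upon inclusion". It adds that allocation is 1:1 and follows eligibility and consent. Blocks, strata and minimization factors are not mentioned there or elsewhere.

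**Route.** Section 5.c admits patients on subcutaneous insulin or infusion, and also patients with a history of diabetes, who need not be on insulin. Section 5.i prefers infusion especially for patients who are NPO, unstable, on inconsistent nutrition or in organ dysfunction. It also says "SC insulin regimen may be used based on the discretion of the treating ICU team", recommends that regimen only for stable patients on consistent nutrition, and foresees conversion from infusion to subcutaneous insulin.

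**Checks in the control arm.** Section 5.m.iii sets point-of-care (POC) checks by route: "Every 1-2 hours per protocol if receiving an insulin infusion" and "At least 3 times per day if receiving a basal:bolus insulin regimen".

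**Size.** Section 5.b: "A minimum sample size was calculated to be a total of 88 patients (44 per group"), though the trial "will continue to enroll patients for a maximum of 2 years or a maximum of 300 patients". The basis is "Anticipated mean POC % time in range of 58% (based on current rates in our facility) with a standard deviation of 20"%, against 70% with CGM, at 80% power and 5% alpha.

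**Analysis.** Section 6 says only that descriptive and inferential methods will be used as appropriate. It names no model, covariate or subgroup.

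**The concern.** Route at enrollment reflects how sick the patient is and how the patient is fed, and it fixes the intensity of the comparator. A variable of that kind probably explains some of the spread in time in range. The plan neither balances it at assignment nor accounts for it in the analysis.

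Two things are at stake. The first is precision: variation due to route stays in the error term of a trial planned at about 80% power with nothing to spare. The second is readability: if the arms differ visibly in route, a later adjustment chosen after seeing the data will be open to question. Route recorded after assignment is not a safe substitute, because the CGM arm is open to the treating team and route may change in response.

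**Working it through.** **1. The plan's own figure.** Inputs from 5.b: difference 70 − 58 = 12, SD 20, power 80%, alpha 5% (two-sided assumed, since sidedness is not stated).
n per arm = 2 × (1.960 + 0.842)² × 20² / 12² = 43.6, rounded up to 44, so 88 in total. This reproduces the plan. The standard error is 20 × √(2/44) = 4.26 points. Power at 44 per arm is 80.4% by the normal approximation and 79.5% by the t-test.

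**2. Chance imbalance in route under simple randomization.** The share on infusion, p, is not in the documents; 30% to 70% is assumed. With n per arm, the SD of the between-arm difference in share is √(2p(1 − p)/n), and p = 0.3 and p = 0.7 give the same value.

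| n per arm | p | SD (points) | P(≥10 points) | P(≥15 points) | P(≥20 points) |
|---|---|---|---|---|---|
| 44 | 0.3 | 9.8 | 29% | 13% | 5% |
| 44 | 0.5 | 10.7 | 34% | 17% | 7% |
| 150 | 0.3 | 5.3 | 7% | 0.5% | <0.1% |
| 150 | 0.5 | 5.8 | 9% | 0.9% | 0.1% |

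These are exact binomial results with equal arms. Letting arm sizes vary at 88 patients gives much the same (31% and 34% for ≥10 points).

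**3. Shift in the primary difference.** Shift = imbalance × gap in mean time in range between routes. The gap is not in the documents. At a 15-point imbalance:
- gap 10: 0.15 × 10 = 1.5 points
- gap 15: 0.15 × 15 = 2.25 points
- gap 20: 0.15 × 20 = 3.0 points

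That is 13% to 25% of the planned 12 points, and 0.35 to 0.70 of the standard error of 4.26.

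**4. Gain from using baseline route.** Taking the planned SD of 20 to describe the mixed population, the SD within route is √(400 − gap² × p(1 − p)). Power for 12 points at 44 per arm, against 80.4% without route:

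| Gap | SD within route | Standard error | Power |
|---|---|---|---|
| 5 | 19.8–19.9 | 4.23–4.24 | 81% |
| 10 | 19.4–19.5 | 4.13–4.15 | 82–83% |
| 15 | 18.5–18.8 | 3.95–4.00 | 85–86% |
| 20 | 17.3–17.8 | 3.69–3.79 | 89–90% |

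**5. Stratify, adjust or both.** Simulation of 8,000 trials per cell, 88 patients, half on infusion:

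| Design and analysis | Type I error, gap 10 | Power, gap 10 | Type I error, gap 20 | Power, gap 20 |
|---|---|---|---|---|
| Neither | 5.1% | 79% | 4.5% | 79% |
| Stratified only | 4.3% | 80% | 2.4% | 83% |
| Adjusted only | 4.9% | 81% | 4.9% | 89% |
| Both | 4.6% | 82% | 5.1% | 90% |

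The mean estimate was within 0.1 point of the true value in every cell.

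**6. Effects by route.** At an even split there are 22 patients per arm in each route. The standard error is 20 × √(2/22) = 6.03, and power for 12 points is about 51%. With the smaller within-route SDs above it is 54% (gap 10) to 63% (gap 20).

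**The case against.** **Chance imbalance is not confounding.** A reader might infer that an excess of infusion patients in one arm would bias the primary comparison or be mistaken for a CGM effect. The documents do not support that. Imbalance from a random draw is random error, the standard error already covers it, and simulated type I error was 4.5% to 5.1%. If the SD of 20 comes from the facility's mixed population, this variation is already in the sample size. This objection stands in full; what remains is lost precision.

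**The draw may not be simple.** A computerized algorithm could include blocks or strata. This also stands: the gap is that the method is unspecified, and the imbalance figures apply only if simple randomization is used.

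**POC frequency is not the source of the shift.** The contrast between checks every 1 to 2 hours and at least 3 a day suggests that the CGM benefit may differ by route. That is effect modification, and balancing route does not change how the mix drives the average effect. Imbalance moves the estimate only through a difference in mean time in range. Three a day is also a floor.

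**A redraw by treating staff is speculation.** A reader might infer it from 5.e: "Study team members are ICU clinicians and may also be part of the team providing clinical care". That sentence concerns recruitment, and nothing says who makes the draw. Concealment is simply not described.

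**Adjustment would nearly suffice.** At a 20-point gap it gives 89% power alone, against 90% with stratification. Section 5.o already collects insulin treatment from the record. This largely stands, but section 6 plans no adjustment, and the route used must be the one in place before assignment.

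**88 is a minimum.** Near 300 patients, the SD of the imbalance falls to 5.3 to 5.8 points and power for 12 points is already above 99%, so the gain is then a narrower interval only.

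**Conclusion.** The point holds as an inexpensive gain in precision and as a gap in specification. It is not a threat to validity. The assignment method is given only by example, and a plausible predictor of the primary outcome is used in neither design nor analysis.

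The gain at 88 patients depends on two figures that the documents do not give: the share on infusion (assumed 30% to 70%) and the route gap in time in range. For gaps of 10, 15 and 20 points, power rises from about 80% to about 82–83%, 85–86% and 89–90%. For a gap of 5 points it is about 81%, so there is almost no gain. If route does not predict time in range, nothing is gained and almost nothing is lost.

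**What to change.** 1. **Before assignment:** record current insulin route as IV infusion versus other. The second level also takes diabetes-history patients who are not on insulin.
2. **Section 5.f.ii:** name the method as permuted blocks of random size (for example 4 and 6), stratified by that recorded route. Have the list loaded by someone who neither enrolls nor treats. Release each assignment through the study's REDCap system (5.p) only after eligibility, consent and route are locked.
3. **Section 6:** pre-specify a primary comparison adjusted for baseline route. Stratifying without adjusting makes the test conservative (2.4% type I error at a 20-point gap). If only one of the two changes is made, adjustment is the one to choose.
4. **By-route estimates:** report them as exploratory, with intervals, given about 50% power per route at an even split.

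**Cost:** one field that must be completed before randomization, plus a one-time list set-up. No extra patients or procedures. The change does not deal with switches of route after assignment, and route recorded later should not be used as a covariate.

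### In the CGM arm the sensor that largely steers treatment also scores the primary outcome, so lasting sensor error makes the contrast overstate the effect on true glucose by an amount the plan does not measure

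*Combined protocol and SAP*

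**What the plan says.** Section 5.h.i defines the primary outcome as percentage of time at 70-180 mg/dL and specifies "Comparison of CGM readings between both types of monitoring/treatment groups". Section 5.g separates the arms by what guides treatment. For the CGM group: "Glycemic management will be based on CGM values". For the POC group, whose sensor is blinded: "Glycemic management will be based on POC glucose values".

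The procedures sections add detail:

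- CGM group (5.n.ii): "All treatment decisions for this group will be based on CGM readings, confirmatory POC readings (as necessary), and venipuncture".
- POC group (5.m.ii): "All treatment decisions for this group will be based on POC readings and venipuncture".
- Check on the sensor in the CGM group (5.n.iii): "Nursing staff will obtain a confirmatory POC for hypoglycemia alarms and administer appropriate therapy per protocol". Section 5.n.vi adds a POC check for LOW readings. No check is required for high or in-range readings.
- Calibration (5.l.i) is allowed when needed, with no schedule.
- Section 5.l.ii plans a correlation of CGM and POC with "routine venipuncture monitoring" at a daily interval, but does not link it to the primary outcome.

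Section 5.i.iii states that "IV insulin infusion targeting BG 140-180 mg/dL is preferred treatment". Appendix D describes the infusion tool as taking a point-of-care value entered by the nurse and does not distinguish the arms. Section 6 names no method or sensitivity analysis for sensor error.

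**The concern.** One instrument is both guide and judge in the CGM arm, and only judge in the POC arm. Suppose a sensor reads 10% low for days and insulin is titrated until it shows 165 mg/dL. True glucose is then 165/0.9 = 183, above range, but the score says in range. In the POC arm the same faulty sensor changes the score and leaves treatment alone. Equal, unbiased accuracy does not remove this difference, because the error acts through treatment in one arm only.

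The stated purpose (section 4) is to compare glycemic control, not sensor readings. A small apparent gain for CGM could accompany equal or slightly worse true time in range, and nothing in the analysis plan would reveal it. The infusion target ends at 180, the upper limit of the outcome range, so modest error can carry values across that limit.

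**Working it through.** **The plan's own figure.** Section 5.b gives means of 58% and 70%, SD 20, 80% power and 5% alpha. Per arm, n = 2 × ((1.960 + 0.842) × 20/12)² = 43.6, so 44 per arm and 88 in total. This reproduces the plan (two-sided, normal approximation). The sample size is not in question.

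**Assumptions.** Sensor error size is not in the documents. Zero-mean error of 5 to 15%, equal in both arms, is assumed. Overstatement means the scored difference minus the true difference (CGM minus POC).

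**Model 1: feedback simulation near 58%.** Five-minute readings over 5 days and hourly titration by the same controller in both arms. The CGM arm is titrated on the sensor, the POC arm on a meter with 5% CV. Both are scored on the sensor. Entries are rounded separately.

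| Sensor error | CGM true / scored | POC true / scored | Scored diff. | True diff. | Overstatement |
|---|---|---|---|---|---|
| none | 59.0 / 59.0 | 58.8 / 58.8 | +0.2 | +0.2 | 0.0 |
| 5% persistent | 58.6 / 59.1 | 58.9 / 58.8 | +0.3 | -0.3 | 0.5 |
| 10% persistent | 57.8 / 59.7 | 58.9 / 58.8 | +0.9 | -1.1 | 2.0 |
| 15% persistent | 56.8 / 60.7 | 58.9 / 58.4 | +2.2 | -2.1 | 4.4 |
| 10%, 12-hour time constant | 57.9 / 59.5 | 58.9 / 59.0 | +0.4 | -1.0 | 1.4 |
| 10%, halved daily by calibration | 58.7 / 59.2 | 58.9 / 58.9 | +0.3 | -0.2 | 0.5 |
| 10%, independent between readings | 59.0 / 59.1 | 58.8 / 58.9 | +0.2 | +0.2 | 0.0 |

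The error has to persist. At 10%, the POC score is 0.1 below truth (58.8 against 58.9), while the CGM score is 1.9 above it (59.7 against 57.8). Nearly all the bias is loss hidden in the CGM arm.

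**Model 2: no dynamics.** The steering reading is X ~ N(mean, SD) in both arms, and each value carries error b ~ N(0, e). POC arm: true = X, scored = X(1+b). CGM arm: scored = X, true = X/(1+b). Example with mean 170, SD 45, e = 15%: X is in range 57.4% of the time, the POC arm scores 57.9 and the CGM arm is truly 56.0. The scored difference is 57.4 - 57.9 = -0.5, the true difference is 56.0 - 57.4 = -1.4, and the overstatement is 0.9. Four settings near 57-58% in range (168/48, 170/45, 172/40, 175/30) give:

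- 5% error: overstatement 0.0 to 0.1
- 10%: 0.2 to 0.4
- 15%: 0.9 to 1.3
- 20%: 2.3 to 2.7

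The scored difference lies between about -0.5 and +0.3 throughout.

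**Tighter and looser control.** In Model 2 at mean 160, SD 30 (75% in range), the overstatement is 5.1 at 10% error and 9.8 at 15%. In Model 1 at about 71-80% in range it is 3.0 to 8.5 at 10%. In Model 2 at mean 170, SD 55 (54% in range) it is about 0 to 0.3 at 10-15%.

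**False significance.** The standard error is 20 × √(2/44) = 4.26 at 88 patients and 20 × √(2/150) = 2.31 at 300. With a two-sided 5% t-test, a spurious scored difference of 1 point is significant in 5.6% of trials at 88 and 7.2% at 300. For 2 points the figures are 7.5% and 13.9%.

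**Precision of a venous comparison.** Assume 4 values per patient, between-patient SD 20 and 58% in range. The variance of a patient's percentage is 400 + (58 × 42 - 400)/4 = 909, so the SD is 30.1. The 95% half-width is 1.96 × 30.1 × √(2/44) = 12.6 points at 88 patients and 1.96 × 30.1 × √(2/150) = 6.8 at 300.

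**The case against.** The strongest reply is that steering in the CGM arm is not by sensor alone. Treatment there also draws on POC confirmation and venipuncture, calibration is allowed, and hypoglycemia alarms and LOW readings require a POC check. If the Appendix D tool takes a POC value in both arms, much of the feedback loop disappears for the preferred treatment. This stands as a limit on size. It does not remove the problem: no check is required for readings that are falsely in range or falsely high, calibration has no schedule, and Appendix D conflicts with sections 5.g and 5.n as written.

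A reader might also infer four stronger things that the documents do not support.

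- That any random sensor error causes the bias. Independent noise gives none.
- That the POC arm is penalised. Near 58% in range the penalty is close to nil and can change sign, because glucose sits near the upper limit and extra spread moves about as much time in as out. A visible penalty appears only under tighter control.
- That an accuracy report by arm could not show the effect. Average error would hide it, but difference against level would not. In Model 2 at mean 165, SD 40 and 15% error, the sensor-to-true SD ratio is 1.19 in the POC arm and 0.80 in the CGM arm.
- That a missed low favours only the CGM arm. A low the sensor misses is scored in range in both arms, and lows between POC checks can also go untreated.

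**Conclusion.** The concern holds in a limited form. The scoring and steering rules differ by arm as described, and no independent reference is tied to the primary outcome. With persistent error of 5 to 15% near the planned 58%, the sensor contrast overstates the effect on true time in range by roughly 0 to 4 points (0.0 to 1.3 in the simple model, 0.5 to 4.4 with feedback).

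This cannot by itself produce the planned 12 points, and a reader should not infer that it could. It can reverse the sign of a small difference: with feedback and 10-15% error, CGM scores 0.9 to 2.2 points better while truly 1.1 to 2.1 worse. False significance rises modestly, to about 6-8% of trials at 88 patients and 7-14% at 300 for a spurious 1 to 2 points.

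All sizes rest on an assumed error level and on largely sensor-based steering. They shrink with calibration or POC-based titration and grow under tighter control.

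**What to change.** 1. Prespecify a supportive comparison by arm, with confidence interval, of each patient's percentage of routine scheduled venous glucose values at 70-180, <70 and >180 mg/dL. Exclude draws triggered by an alarm or a CGM-POC disagreement; section 5.n prescribes these in the CGM arm only, so they would load that arm's sample with suspected lows.
2. Report the paired sensor-venous data by arm as difference against level (Bland-Altman slope or SD ratio), not only as correlation or average error.
3. Word the primary conclusion as time in range by sensor readings. Extend it to glycemic control only with the venous estimate and its interval shown alongside. Do not require the two results to agree in direction: such a rule would pass 50% of the time with no true effect, and about 38% (88 patients) or 28% (300) at a true difference of -2 points.
4. Reconcile sections 5.g and 5.n (treatment on CGM values) with Appendix D (POC value entered in the infusion tool), since this determines how large the effect can be.

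The cost is plan wording, a flag for the reason for each venous draw, and two analyses of blood glucose data already listed for collection in section 5.o. No new procedure or change in sample size is needed. The downside is imprecision (half-width about 13 points at 88 patients and 7 at 300). Venipuncture also informs care in both arms, so the venous comparison is supportive and not a replacement.
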